Appendix 8. Study Procedures After Primary Completion Date (PCD) Until End of
Trial..... 182

SCHEDULE OF ACTIVITIES (PART 1, PART 2 AND J-LIC)

The schedule of activities table provides an overview of the protocol visits and procedures. Refer to the [ASSESSMENTS](#) section of the protocol for detailed information on each assessment required for compliance with the protocol.

The investigator may schedule visits (unplanned visits) in addition to those listed in the schedule of activities in order to conduct evaluations or assessments required to protect the well-being of the patient.

See [Appendix 6](#) for alternative measures during public emergencies including the COVID-19 pandemic.

Protocol Activity	Screening	Active Treatment Phase [†] - One Cycle = 28 days					End of Treatment/ Withdrawal [§]	Post-Treatment Follow-Up [*]
		Cycles 1 and 2			Cycles ≥3			
Study Day	Within 28 days prior to registration unless specified otherwise	Day 1 [‡]	Day 8	Day 15	Day 21	Day 1		
Visit Window				±3 days	±3 days	±3 days	±5 days	
Informed Consent ¹	X							
Medical/Oncological History ²	X							
Baseline Signs/Symptoms ³		X						
Physical Examination ⁴	X						X	
Abbreviated Physical Examination ⁵		X	X	X	X	X		X
Vital Signs ⁶	X	X	X	X	X	X	X	X
Contraception Check ⁷	X	X				X	X	
ECOG Performance Status ⁸	X	X				X	X	X
12-Lead ECG ⁹	X	X	X C1 ⁹ and C2 ⁹	X C1 only		X	X	
Laboratory Studies¹⁰								
Hematology	X	X	X	X	X	X	X	(X)
Blood Chemistry	X	X	X ¹¹	X ¹¹	X ¹¹	X	X	(X)
Coagulation	X	X						(X)
Urinalysis	X						X	(X)
Pregnancy test	X	X				X	X	
Viral disease screening ¹²	X							
Disease Assessment								
Tumor markers (for breast cancer: CA 15-3 and CEA; Part 1 only for ovarian cancer: CA 125)	X	X				X	X	
CT/MRI Scans of Chest, Abdomen, Pelvis, any clinically indicated sites of	X	Performed every 8 weeks from C1D1 (±7 days) for the first 6 months, and then every 12 weeks (±7 days)					X ¹³	

Protocol Activity	Screening	Active Treatment Phase [†] - One Cycle = 28 days					End of Treatment/ Withdrawal [§]	Post-Treatment Follow-Up [*]
		Cycles 1 and 2				Cycles ≥3		
Study Day	Within 28 days prior to registration unless specified otherwise	Day 1 [‡]	Day 8	Day 15	Day 21	Day 1		
Visit Window			±3 days	±3 days	±3 days	±5 days		±7 days
disease, and of bone lesions; Clinical evaluation of superficial disease ¹³ Follow up for Overall Survival (OS)		thereafter for up to 2 years. After 2 years, performed every 4 months thereafter.						
Study Treatment								

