2.1. Study Design

This is a Phase I/2a, open-label, multi-center, non-randomized, multiple dose, safety, tolerability, pharmacokinetic, and pharmacodynamic study of PF-06873600 administered as a single agent in sequential dose levels and then in combination with endocrine therapy. In Part IA, successive cohorts of patients will receive escalating doses of PF-06873600 starting at 1 mg BID dosed on a continuous basis and then in dose finding (Part IB) with immediate release formulations of PF-06873600 in combination with endocrine therapy (ET) in an outpatient setting. In Part IC, successive cohorts of patients will receive escalating doses of PF-06873600 testing a modified release (MR) formulation in a MR cohort evaluation and then in dose finding (Part IB) with modified release formulations of PF-06873600 in combination with endocrine therapy (ET) in an outpatient setting.

This study contains 2 parts, dose escalation with single agent (Part IA and IC) and then dose finding with PF-06873600 in combination with endocrine therapy (letrozole and fulvestrant, independently with both immediate and modified release formulations) (Part IB) followed by dose expansion arm in combination with endocrine therapy (Part 2). The overall study design is depicted in Figure 1 and Figure 2 below.

The Japan lead-in cohort (J-LIC) will be added separately as a sub-cohort in order to assess the safety of monotherapy of PF-06873600 in Japanese population. Detailed information is provided in the Appendix 7. Japanese participants will be able to enroll into Part 2 after safety and tolerability of monotherapy of PF-06873600 in Japanese participants is confirmed.

In Part IA, Part IB, and Part IC patients will participate in a dose escalation/finding phase aimed at estimating the MTD. The sample size for this component of the study will vary depending on the number of DLTs observed.

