- **Duration of Response (DOR):** Time from the date of first documentation of CR or PR to the date of first documentation of objective progression or death due to any cause.
- **Time to Progression (TTP):** Time from randomization until disease progression.

More details of censoring are provided in [Appendix 3](#).

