9.2.2. Secondary Analyses

9.2.2.1. Efficacy Analysis

Overall this First-in-Patient study anti-tumor activity is a primary objective for Part 2 of the study. Tumor response will be presented in the form of patient data listings that include, but are not limited to, tumor type, starting dose, tumor response at each visit, and best overall response. In addition, progression date, death date, date of first response and last tumor assessment date, and date of last contact will be listed. Objective response rate (ORR), progression-free survival (PFS), time to progression (TTP), and duration of response (DOR) will be summarized and presented. The definition of each response category is provided in [Appendix 2](#) (RECIST 1.1).

Efficacy analysis will be summarized by dose cohorts for Part 2 of the study (dose expansion). For Part 1 (dose escalation), no formal efficacy analysis will be presented; instead, results will be listed.

For response-based metrics (BOR, ORR and DOR), analyses will be presented based on confirmed responses. Analysis of progression free survival and time to progression are defined as time from the date of first dose. Summaries of the number and percentage of subjects with PFS, and TTP and data listing by tumor type and dose will be generated. If applicable, the PFS may also be summarized using the Kaplan-Meier method at all or some of the following timepoints: PFS, DOR, and TTP at 3, 6, 9, 12, 18, and then every 6 months.

The 95% confidence intervals will be generated. Confidence intervals for medians and quartiles will be based on the Brookmeyer-Crowley method. Confidence intervals for the estimated probability of an event at a particular time point will be generated using the

Greenwood formula. Duration of response will be summarized with number of responders, number and percentage of event/censorship, mean, standard deviation, minimum, maximum and median of duration in unit of months. ORR will be summarized by number of subjects meeting respective criteria, percentage. The 95% confidence intervals will be generated for PFS, TTP, and ORR. Definitions of PFS, TTP, DOR, and ORR are outlined in section 7.1 of this SAP. Supportive figures depicting the change in tumor size may also be provided.

The following table provides an overview of the efficacy analysis.

Table 3 Summary of Efficacy Analysis

Endpoint	Analysis Set	Statistical Method	Model/Covariates/Strata	Missing Data	Interpretation

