All sites of disease must be assessed at baseline. Baseline assessments should be done as close as possible prior to study start. For an adequate baseline assessment, all required scans must be done within 28 days prior to randomization and all disease must be documented appropriately. If baseline assessment is inadequate, subsequent statuses generally should be non-evaluable.

Target Lesions

All measurable lesions up to a maximum of 2 lesions per organ, 5 lesions in total, representative of all involved organs, should be identified as target lesions at baseline. Target lesions should be selected on the basis of size (longest lesions) and suitability for accurate repeated measurements. Record the longest diameter for each lesion, except in the case of pathological lymph nodes for which the short axis should be recorded. The sum of the diameters (longest for non-nodal lesions, short axis for nodal lesions) for all target lesions at baseline will be the basis for comparison to assessments performed on study.

- If two target lesions coalesce the measurement of the coalesced mass is used. If a large target lesion splits, the sum of the parts is used.
- Measurements for target lesions that become small should continue to be recorded. If a target lesion becomes too small to measure, 0 mm should be recorded if the lesion is considered to have disappeared; otherwise a default value of 5 mm should be recorded.

NOTE: When nodal lesions decrease to <10 mm (nodal), the actual measurement should still be recorded.

Non-target Disease

All non-measurable disease is non-target. All measurable lesions not identified as target lesions are also included as non-target disease. Measurements are not required but rather assessments will be expressed as CR, Non-CR/Non-PD, PD, Non-evaluable (NE). Multiple non-target lesions in one organ may be recorded as a single item on the case report form (eg, 'multiple enlarged pelvic lymph nodes' or 'multiple liver metastases').

OBJECTIVE RESPONSE STATUS AT EACH EVALUATION

Disease sites must be assessed using the same technique as baseline, including consistent administration of contrast and timing of scanning. If a change needs to be made the case must be discussed with the radiologist to determine if substitution is possible. If not, subsequent objective statuses might be non-evaluable.

Target Disease

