- If CR determination depends on a residual lesion that decreased in size but did not disappear completely, it is recommended the residual lesion be investigated with biopsy or fine needle aspirate. If no disease is identified, objective status is CR.

- If progression determination depends on a lesion with an increase possibly due to necrosis, the lesion may be investigated with biopsy or fine needle aspirate to clarify status.

Subjective Progression

Patients requiring discontinuation of treatment without objective evidence of disease progression should not be reported as PD on tumor assessment CRFs. This should be indicated on the end of treatment CRF as off treatment due to Global Deterioration of Health Status. Every effort should be made to document objective progression even after discontinuation of treatment.

Table 4 Objective Response Status at each Evaluation

Target Lesions	Non-target Disease	New Lesions	Objective status
CR	CR	No	CR
CR	Non-CR/Non-PD	No	PR
CR	NE or Missing	No	PR
PR	Non-CR/Non-PD, NE or Missing	No	PR
SD	Non-CR/Non-PD, NE or Missing	No	Stable
NE or Missing	Non-PD	No	NE
PD	Any	Yes or No	PD
Any	PD	Yes or No	PD
Any	Any	Yes	PD

If the protocol allows enrollment of patients with only non-target disease, the following table will be used:

Table 5 Objective Response Status at each Evaluation for Patients with Non-Target Disease Only

Non-target Disease	New Lesions	Objective status
CR	No	CR
Non-CR/Non-PD	No	Non-CR/Non-PD
NE	No	NE
Unequivocal progression	Yes or No	PD
Any	Yes	PD

Best Overall Response

The best overall response (BOR) is the best response recorded from the randomization until disease progression or death due to any cause. This is derived from the sequence of objective

statuses. Objective statuses are not considered after objective progression is documented or after start of the first anticancer treatment post discontinuation of protocol treatment. BOR for each patient will be derived as one of the following categories.

- **Complete response (CR):** At least one objective status of CR documented before progression.
- **Partial response (PR):** At least one objective status of PR documented before progression.
- **Stable disease (SD):** At least one objective status of stable documented at least 8 weeks after randomization date and before progression but not qualifying as CR, PR.
- **Progressive Disease (PD):** Objective status of progression within 16 weeks of randomization, not qualifying as CR, PR or SD.

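### SAP times TTP, baseline-scan adequacy and best-response windows from a randomization that does not exist, and its 16-week PD/NE limit ignores the ±7-day scan window

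*SAP*

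**What the plan says.** SAP 2.1 describes the study as "open-label, multi-center, non-randomized, multiple dose". SAP 7.1 nevertheless defines TTP as "Time from randomization until disease progression".

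SAP Appendix 2 uses the same event for three further rules:

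- **Baseline adequacy:** "all required scans must be done within 28 days prior to randomization and all disease must be documented appropriately". If this fails, later statuses are generally to be treated as non-evaluable, and SAP Tables 6 and 7 censor a patient with an inadequate baseline at C1D1.
- **Start of best overall response.**
- **The SD, PD and NE windows.** SD needs a stable status at least 8 weeks after randomization. PD is "Objective status of progression within 16 weeks of randomization, not qualifying as CR, PR or SD". NE is the complement at the same 16 weeks.

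Protocol Appendix 4 repeats these Appendix 2 rules, except that its SD minimum is 6 weeks.

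Other sections name different dates:

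- **TTP:** SAP 9.2.2.1 states "Analysis of progression free survival and time to progression are defined as time from the date of first dose", but later in the section adds "Definitions of PFS, TTP, DOR, and ORR are outlined in section 7.1 of this SAP", which leads back to randomization. Table 7 uses C1D1 as its start date.
- **Best response:** SAP 7.1 starts it at first dose.
- **Screening scans:** the protocol Schedule of Activities (Part 1, Part 2 and J-LIC) gives "Within 28 days prior to registration unless specified otherwise".
- **On-study scans:** the same schedule runs them every 8 weeks from C1D1, ±7 days, for the first 6 months.

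**The concern.** These are operative rules, and as written they refer to a date that no patient has. Whoever programs them must substitute one, and the SAP contradicts itself on TTP and on best response. The substitution matters most for baseline adequacy, because a failed baseline triggers censoring at C1D1 in both Table 6 and Table 7.

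Replacing the word does not cure everything. Even when counted from C1D1, the 16-week PD/NE limit closes in the middle of the permitted window for the week-16 scan. A patient scanned on schedule whose disease has progressed can then be reported as non-evaluable.

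**Working it through.** The documents give no figure to reproduce. The check is date arithmetic in whole elapsed days, with C1D1 as day 0 and registration at day −g (g ≥ 0). The documents do not give g.

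**Inputs**

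- Screening scan: up to 28 days before registration (Schedule of Activities).
- Week-8 scan: 56 ± 7, so days 49 to 63. Week-16 scan: 112 ± 7, so days 105 to 119 (Schedule of Activities).
- PD/NE limit: 16 × 7 = 112 days (SAP Appendix 2).
- SD minimum: 8 × 7 = 56 days (SAP Appendix 2) or 6 × 7 = 42 days (Protocol Appendix 4).

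**1. Baseline rule run from C1D1**

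The oldest compliant scan is 28 + g days old at C1D1: 29 at g = 1, 31 at g = 3, 35 at g = 7. It exceeds 28 days whenever g ≥ 1. Run from registration, the oldest compliant scan is 28 days old and always passes.

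**2. PD/NE limit run from C1D1**

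Permitted week-16 days: 119 − 105 + 1 = 15. Days past the limit: 113 to 119, which is 7. The share is 7/15 = 47% of permitted days. This is a share of calendar days, not of patients.

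Run from registration, the latest on-schedule week-16 scan falls at 119 + g days. The days lost are 7 + g for g up to 8: 8/15 at g = 1, 10/15 at g = 3, 14/15 at g = 7.

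**3. When PD on days 113 to 119 becomes NE (limit run from C1D1)**

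This happens only if no CR, PR or SD already qualifies. There are two routes:

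- The first scan was missed or non-evaluable.
- The first scan was stable but fell on days 49 to 55, so the SAP 8-week minimum rejects it. Example: stable on day 50, PD on day 115. Of 15 × 15 = 225 permitted date pairs, 7 × 7 = 49 (21.8%) do this. Under the protocol's 6-week minimum the count is 0, because 49 ≥ 42.

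**4. Does the SAP allow for scan windows elsewhere?**

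The 18- and 26-week missed-scan limits in SAP 7.1 equal 2 × 8 + 2 and 2 × 12 + 2 weeks, that is, two scan intervals plus two weeks. The 16-week limit equals 2 × 8 with nothing added.

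**5. What the mislabelling changes**

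PD and NE are both non-responses, so the responder count is unchanged. PFS and TTP events come from progression and death dates under their own censoring rules (SAP 7.1, Tables 6 and 7), not from the best-response category. What changes is the split between PD and NE in the best-overall-response table.

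**The case against.** The strongest reply is that each rule has a sensible date elsewhere. SAP 9.2.2.1 and Table 7 point to first dose or C1D1 for TTP, and in Part 2 these coincide. SAP 7.1 gives first dose for best response. The Schedule of Activities ties screening scans to registration. A careful programmer would probably choose these. That stands, and it limits the harm. It does not remove the contradiction, since 9.2.2.1 itself sends the reader back to the randomization wording and nothing says which passage governs.

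A reader might go further in three ways that the documents do not support:

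- **Responders are lost from the Part 2 ORR.** This needs a C1D1 reading of the baseline rule, which the Schedule of Activities contradicts. It also needs the qualified wording on non-evaluable statuses to override the investigator's recorded response. SAP 7.1 derives efficacy from the investigator's CRF evaluation, and no passage orders such recoding.
- **A known share of patients is affected.** If scan dates were spread evenly over 28 days, the share of baselines failing from C1D1 would be g/28: 3/28 = 11% or 7/28 = 25%. Both the even spread and the gap are assumptions, so these figures are illustrative only.
- **The rules are unworkable because no one date fits them all.** Arithmetically, accepting every compliant baseline needs an origin no later than day −g, while covering day 119 within 112 days needs one no earlier than day +7. But nothing requires a single date. Each rule can have its own.

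It is also fair that the 16-week problem is separate from the randomization wording, and that the analyses are estimation only.

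**Conclusion.** The point holds in two limited parts.

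First, TTP, baseline-scan adequacy and the best-response windows are anchored to an event the trial does not have. For TTP and best response the SAP contradicts itself; for baseline scans it departs from the Schedule of Activities. If the baseline rule were run from C1D1, a compliant patient could be censored at C1D1 for PFS and TTP with as little as a one-day gap between registration and dosing. The number affected cannot be derived from the documents.

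Second, the 16-week PD/NE limit is too short for the plan's own scan schedule whichever of these dates is used. From C1D1 it excludes 7 of 15 permitted week-16 days. The 8-week SD minimum in the SAP widens the exposure to patients who had an evaluable, on-schedule first scan; the protocol's 6 weeks would not. The 47% and 21.8% count permitted dates equally and do not predict how many patients are mislabelled.

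Severity is minor to moderate: a real inconsistency in operative rules with a demonstrable effect on the best-overall-response table, and no demonstrated effect on ORR.

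**What to change.** Edit SAP 7.1 and Appendix 2, and mirror the Appendix 2 changes in Protocol Appendix 4 at its next update:

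1. Anchor the 28-day baseline-scan rule to registration, as in the Schedule of Activities.
2. Anchor TTP and all best-overall-response windows to C1D1, stating that this is the date of first dose in Part 2. In the Part 1C modified-release selection cohort the first dose is on Day −7, so the text should say C1D1 explicitly. Part 1 efficacy is only listed, so little depends on it.
3. Set the PD/NE limit at 17 weeks from C1D1 (17 × 7 = 119 days, the last permitted day of the week-16 scan).
4. Align the SAP's 8-week SD minimum with the protocol's 6 weeks, so that any in-window week-8 scan counts.

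Steps 3 and 4 are needed as well as 1 and 2, because replacing the word randomization alone leaves the PD/NE mislabelling in place. The cost is text and programming specification only; no new data are required.

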7.2. Safety Endpoints

7.2.1. DLT Definitions

Severity of adverse events (AEs) will be graded according to Common Terminology Criteria for Adverse Events (CTCAE) version 4.03. The definition is provided in Section 3.1.6. of the protocol.

7.2.2. MTD Definition

The MTD is defined as the highest dose associated with a DLT rate of 27.5% with an equivalence interval of (22.5%, 32.5%) following the mTPI method. During dose escalation/finding, patients will be enrolled in dose cohorts of 1-4 patients in Part JA and 2-4 patients in Part 1B and Part 1C in dose cohorts other than the MTDIRDE. Each MTDIRDE including single-agent and combination treatments will enroll 6-12 patients. Each patient will receive continuous doses of PF-06873600 every 28 days. The dose finding decision will be based on J-cycle (28 days) DLT observation period. DLTs observed after the Cycle 1 (28-day) may also be considered in the final determination of the MTD as a single agent, in combination with letrozole, and in combination with fulvestrant.

7.2.3. Recommended Dose for Expansion (RDE) and Recommended Phase 2 Dose (RP2D) Definition

The RDE is the dose chosen for further investigation based on Part 1 study results. If the RDE proves to be clinically feasible for long-term administration in a reasonable number of patients, then this dose usually becomes the RP2D. Further experience with the RDE may result in a RP2D dose lower than the RDE. A RP2D for PF-06873600 as a single agent, in combination with letrozole, and in combination with fulvestrant are planned to be individually determined based on the respective RDE/MTD and other considerations including available pharmacodynamic, pharmacodynamic, and clinical benefit data.

7.2.4. Vitals Signs

Vital signs to be obtained include temperature, blood pressure and pulse rate. See Schedule of Activities in the protocol for details.

7.2.5. Laboratory Data

Screening labs to be performed within 7 days of CJD1. Laboratory assessments can be performed earlier but will have to be repeated to be done within 7 days of CJD]. For subsequent cycles, pre-dose labs may also be drawn up to 3 days (-3 days/72 hours) in advance of scheduled dosing in order to obtain results prior to visit.

The laboratory results will be graded according to the NCI CTCAE v4.03 severity grade. For labs for which an NCI CTCAE v4.03 scale does not exist, the frequency of patients with values below, within, and above the normal ranges will be summarized by dose. Baseline evaluations for laboratory data are those collected:

- Within 28 days prior to Cycle 1/Day 1.
- Closest but prior to Cycle 1/Day 1 if there is more than one baseline evaluation.

7.2.6. Adverse Events

Assessment of adverse events will include the type, incidence, severity (graded by the National Cancer Institute Common Terminology Criteria for Adverse Events [NCI CTCAE] version 4.03) timing, seriousness, and relatedness.

All AEs will be coded by system organ class (SOC) and preferred term using Medical Dictionary for Regulatory Activities (MedDRA). The severity of all AEs will be graded by the investigator using NCI CTCAE Version 4.03 whenever possible. For other AEs without specific CTC definitions, results are identified according to CTCAE "other" categories. Adverse events will be assigned to the appropriate cycle based on Day 1 of each cycle.

Treatment Emergent Adverse Events

An adverse event is considered a Treatment-Emergent Adverse Event (TEAE) if the event started during the effective duration of treatment (i.e., from the first dose of study treatment until last dose of study treatment+ 28 days or start of new anti-cancer therapy - 1 day, whichever occurs first).

Treatment Related Adverse Events

Treatment Related Adverse Events are treatment emergent adverse events with cause categorized by the investigator as related to study treatment. Events that are continuations of baseline abnormalities (signs and symptoms) are not considered treatment emergent, and hence are not considered treatment related, unless there is an increase in grade over baseline.

